# 6.3 Procedures for Monitoring Subject Compliance

In order to maintain the investigator-blind, administration compliance will be assessed by dedicated personnel based on measurement of unused preparation and fluid intake recorded by the subject/caregiver on the subject's leaflet. Data collected on the subject's leaflet will be reviewed outside of the colonoscopist's presence and will not be made available to the colonoscopist.

Data will be entered in the eCRF by unblinded personnel as single data entry (one person enters the data in the eCRF). Data verification will be performed by study monitor during on site visits.

**PAGE 46/103** 

#### 7 ASSESSMENT OF EFFICACY

For the timing of assessments in this study, refer to the schedule in Table 4.

# 7.1 Primary Efficacy Endpoints and Evaluations

The primary efficacy endpoints are presented in Section 3.2.1.

Blinded overall assessment of preparation efficacy will be determined by the colonoscopist upon completion of the examination, based on the 4-point scale score presented in Section 7.3.1.

# 7.2 Secondary Efficacy Endpoints and Evaluations

Secondary efficacy endpoints and evaluations are summarised in Table 7.

**Table 7** Secondary Endpoints and Evaluations

Endpoint	Timepoint	Evaluation
Colon cleansing	Visit 2 (Colonoscopy)	Cleansing Score assessed on 4 levels (4-point scale (see Section 7.3.1)
Overall and segmental cleansing assessed by BBPS	Visit 2 (Colonoscopy)	BBPS (see Section 7.3.2.1) Overall score [14]. Segmental score (left colon (LC), transverse colon (TC), right colon (RC)).
Time to clear effluent	Treatment	Time between first intake of prescription and first clear watery stool.
Complete procedure	Visit 2 (Colonoscopy)	Number (%) of complete procedures defined as procedures that reached the caecum
Duration of intubation	Visit 2 (Colonoscopy)	Time between the colonoscope introduction and the time to reach caecum
Duration of examination	Visit 2 (Colonoscopy)	Duration of colonoscope withdrawal from caecum
Need for rescue treatment because of inadequate preparation intake.	Visit 2 (before colonoscopy)	Number (%) of procedures that need a rescue treatment (saline enema)
Treatment acceptability	Treatment	Level of acceptability of treatment assessed using a 5-point Treatment Acceptability Questionnaire (see Section 7.3.2.3).
Need for nasogastric tube	Treatment	Number (%) of subjects who need a nasogastric tube to complete preparation
Treatment compliance	Treatment	Volume of fluid not taken (see Section 7.3.2.2)

# 7.3 Methods and Timing of Assessing, Recording, and Analysing Efficacy Data

Methods for assessing efficacy data are described below. Timing of efficacy assessments are discussed in Section 5. Procedures for recording efficacy data are discussed in Section 14.1 and methods of analyses are discussed in Section 10.4.5.

**PAGE 47/103** 

# 7.3.1 Primary Efficacy Assessment

The primary efficacy variable is the proportion of subjects with successful overall preparation. The colonoscopist will be asked to score the quality of the bowel preparation using the following Cleansing Score (Table 8).

**Table 8** Cleansing Score

Score	Grade	Description
1	Poor	Large amounts of faecal residue, additional cleansing required
2	Fair	Enough faeces or fluid to prevent a completely reliable examination
3	Good	Small amounts of faeces or fluid not interfering with examination
4	Excellent	No more than small bits of adherent faeces/fluid

Primary efficacy will be assessed on the basis of preparation success or failure.

Only perfect preparations graded as excellent (4) or good (3), which allow full, reliable examination of the mucosa, will be considered as successful.

# 7.3.2 Secondary Efficacy Assessment

# 7.3.2.1 Boston Bowel Preparation scale

The overall and segmental cleansing as assessed by BBPS [15] is presented in Table 9.

 Table 9
 Boston Bowel Preparation Scale

Score per segment	BBPS definition
0	Unprepared colon segment with mucosa not seen due to solid stool that cannot be cleared
1	Portion of mucosa of the colon segment seen, but other areas of the colon segment not well seen due to staining, residual stool and/or opaque liquid.
2	Minor amount of residual staining, small fragments of stool and/or opaque liquid, but mucosa of colon segment seen well.
3	Entire mucosa of colon segment seen well with no residual staining, small fragments of stool and/or opaque liquid

This information (segmental cleansing) will be collected for the right, transverse and left colon. Scores per segment will be summed to provide overall cleansing score.

# 7.3.2.2 Treatment/Compliance

The treatment questionnaire will be completed by the caregiver or subject after the subject completes each dose of preparation. The subject/caregiver will provide information about treatment preparation, residual volumes of preparation (volumes not taken by the subject) and start and stop times of intake. For the Eziclen®/Izinova® treatment only, information about the residual volume of water will be reported.

PAGE 48/103

# 7.3.2.3 Treatment Acceptability Questionnaire

The Treatment Acceptability Questionnaire will be completed by the caregiver or subject after the subject completes each dose of preparation. Caregivers will be asked to rate subject acceptability using the following categories (Table 10).

Table 10 Treatment Acceptability Questionnaire Categories

Very badly accepted/unacceptable	Subject showed great displeasure, compromising use of formulation
Badly but accepted	Subject showed displeasure with dosing but could be coaxed to take complete dose
Neither good nor bad	Subject showed no apparent displeasure and with little effort was coaxed to take complete dose
Well accepted	Subject appeared to enjoy the formulation and with little coaxing ingested complete dose
Very well accepted	Subject appeared eager and ingested complete dose without special coaxing

PAGE 49/103

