- Urine analysis by dipstick (pH, protein, ketones, bilirubin, blood, urobilinogen, nitrites, leukocytes, glucose and specific gravity, urine microscopic examination
- Blood and urinary samples for sulphate measurement
- Blood pregnancy test, if female of child-bearing potential. Urine pregnancy test will be performed only when blood tests including pregnancy have been performed prior to Visit 1.
- Indication(s) for colonoscopy to be collected
- Randomisation
- Drug accountability, study treatment dispensation by study nurse (with explanation of treatment administration)
- Subject/caregiver questionnaires dispensation by study nurse (with explanation of questionnaires including compliance measurement)
- Prior and concomitant medications including supplements, herbal medications and nonprescribed compounds
- Prior and concomitant non-drug therapies and surgical procedures
- Collection of AEs from the time of informed consent signature
- Subject status at the end of the visit

Records up to the time of premature termination should be completed. In the event that the subject was not receiving IMP, the primary reason will be recorded.

If any Visit 1 serum chemistry result is considered abnormal and clinically significant by the investigator result may be checked per investigator's decision. The abnormal significant result will be reported as an AE.

In case of non-inclusion of the subject, the primary reason will be recorded.

Following confirmation of eligibility for the study, subjects will be given a randomisation/treatment allocation number and allocated to one of the dosing groups specified in Section 6.1.

Caregivers and subjects will be provided with a subject leaflet containing instructions on how to administer the study preparation. Caregivers will be provided with a Treatment Acceptability Questionnaire (see Section 7.3.2.3) to report their child's experience with the study preparation, and a Symptom Scale to rate subject tolerability (see Section 8.6). Subjects/caregivers will complete these questionnaires during and after the treatment administration.

Subjects will be hospitalised for preparation. The treatment will be prepared by a nurse and administration will be monitored as described in Section 3.4. The nurse or caregiver will fill in

PAGE 42/103

the questionnaires or ensure that the subject fills in, as appropriate. If a subject is unable to complete the preparation, a nasogastric tube will be placed.

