Time between the last intake of fluids and the start of colonoscopy procedure (hours)	V1 (Treatment) and V2 (Colonoscopy)	Time between the end of treatment administration and the start of colonoscopy.

Table 2 Secondary Endpoints and Evaluation	ions
----------------------------------------------------	------

The overall and segmental cleansing as assessed by BBPS [1] is presented in Table 3.

 Table 3
 Boston Bowel Preparation Scale

Score per segment	BBPS definition
0	Unprepared colon segment with mucosa not seen due to solid stool that cannot be cleared
1	Portion of mucosa of the colon segment seen, but other areas of the colon segment not well seen due to staining, residual stool and/or opaque liquid.
2	Minor amount of residual staining, small fragments of stool and/or opaque liquid, but mucosa of colon segment seen well.
3	Entire mucosa of colon segment seen well with no residual staining, small fragments of stool and/or opaque liquid

Scores for the right colon (RC), transverse colon (TC) and left colon (LC) will be collected. Scores per segment will be summed to provide overall cleansing score.

The Treatment Acceptability Questionnaire will be completed by the caregiver or subject after the subject ends the intake of preparation. Caregivers will be asked to rate subject acceptability using the following categories (Table 4).

Very badly accepted/unacceptable	Subject showed great displeasure, compromising use of formulation
Badly but accepted	Subject showed displeasure with dosing but could be coaxed to take complete dose
Neither good nor bad	Subject showed no apparent displeasure and with little effort was coaxed to take complete dose
Well accepted	Subject appeared to enjoy the formulation and with little coaxing ingested complete dose
Very well accepted	Subject appeared eager and ingested complete dose without special coaxing

Table 4 Treatment Acceptability Questionnaire Categories

The compliance will be assessed from the treatment questionnaire which will be completed by the caregiver or subject after the subject ends the intake of preparation. The subject/caregiver will provide information about treatment preparation, residual volumes of preparation (volumes not taken by the subject) and start and stop times of intake. For the Eziclen®/Izinova® treatment only, information about the residual volume of water will be reported.

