3.2.1.2.9 Treatment acceptability

The treatment acceptability at the time of intake after dose 1 and after dose 2 will be assessed by a Treatment Acceptability Questionnaire completed by the caregiver or the subject using a

5-point scale questionnaire (see Table 4). It will be tabulated for each dose and overall (by taking the average of the 2 doses then considered as a score as follows: 1= Very badly accepted/unacceptable, 2= Badly but accepted, 3= Neither good nor bad, 4= Well accepted and 5= Very well accepted) by treatment group.

The acceptability for each dose will be assessed using frequency count with two-sided 95 % CI and analysed using Cochran-Mantel-Hænszel (CMH) chi-square for the proportions adjusting for country effect. The row mean scores differ statistic will be used to assess the test significance.

The SAS Freq procedure will be used as follows:

```
proc freq data=ADQS(where=(QSCAT='TREATMENT ACCEPTABILITY
QUESTIONNAIRE' and PARAMCD in ('TRTA011','TRTA012') and ITTFL='Y'));
table COUNTRYC*TRTP*QSORRES / CMH;
by QSGRPID;
```

run;

The p-value of difference will be summarised.

The overall acceptability will be presented by treatment group using descriptive summary statistics (mean, SD, median, quartiles and ranges) and using a two-way ANOVA including treatment and country as well as the interaction between treatment and country, if it is significant (i.e. p < 0.10), as covariates using the following SAS code:

```
proc mixed data=ADQS(where=(QSCAT='TREATMENT ACCEPTABILITY QUESTIONNAIRE' and PARAMCD='TRTA01' and ITTFL='Y'));
```

```
class TRTP COUNTRYC;
model COMPLIPCT = TRTP COUNTRYC TRTP*COUNTRYC;
by ASPID;
```

lsmeans TRTP / diff cl;

run;

The adjusted mean score, the adjusted treatment difference with their 95 % CI and the p-value of difference will be summarised.

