3.2.3 Missing data and outliers

3.2.3.1 Missing data

No missing value will be replaced, except for the primary analysis where the missing preparation evaluations (because of colonoscopy not done because of inadequate preparation or preparation-related AEs) will be considered as failures.

In the description of qualitative parameters, subjects with a value counted as "missing" at a visit will be identified as subjects being not assessed.

If a value required a retest, the last reliable non-missing value will be taken into account if measured before the first intake of treatment; and the first non-missing reliable value for postbaseline assessments. An assessment will be considered reliable if it is performed without any technical problem and if the result is within the range of plausible values. Any retest or unscheduled assessments performed will be included in the individual subject data listings.

If there is a significant number of missing values for a subject (or if there is confirmed data appearing spurious), a decision will be made following consultation with the sponsor regarding the handling of these data in summaries, prior to database freeze.

Any repeat or additional assessments performed will be included in the individual subject data listings.

3.2.3.2 *Missing or incomplete dates*

In all listings, missing or incomplete dates should be left as they have been recorded. However, for calculation / sorting / assignation based on dates, the following methods will be used:

- The most conservative approach will be systematically considered (i.e. if the onset date of an AE/concomitant medication is missing / incomplete, it is assumed to have occurred during the study treatment phase (i.e. a TEAE for AEs) except if the partial onset date or other data [stop date, ...] indicates differently).
- A missing/incomplete date of medical history or disease diagnosis will be assumed to have occurred before any study treatment.
- If a partial date and the associated information do not allow to state about the assignation to a group / category, all the possible groups / categories will be considered (e.g. a medication with partial start and stop dates could be considered as prior and concomitant treatment).

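### No rule covers acceptability when dose 2 is never started, so subjects who refuse it leave the dose-2 and overall acceptability comparisons

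*Protocol*

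**What the plan says.** **Timing of the forms.** Protocol 7.3.2.3 states: "The Treatment Acceptability Questionnaire will be completed by the caregiver or subject after the subject completes each dose of preparation". Protocol 7.3.2.2 uses the same timing for the intake form: "The treatment questionnaire will be completed by the caregiver or subject after the subject completes each dose of preparation". SAP 1.4.2.1 places both forms "after the subject ends the intake of preparation". The Visit 1 procedures in protocol 5.2.2 are looser again: "Subjects/caregivers will complete these questionnaires during and after the treatment administration". Protocol Table 5 lists the forms as during or after each dose.

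**Scoring.** SAP 3.2.1.2.9 says of acceptability: "It will be tabulated for each dose and overall (by taking the average of the 2 doses", with the categories scored 1 to 5. Each dose is tested separately with a country-adjusted CMH test, and the overall score with an ANOVA. No derivation is given for a subject with only one rating, and the derived-data list in SAP Appendix 1 has no entry for the overall score.

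**Missing data.** SAP 3.2.3.1 begins: "No missing value will be replaced, except for the primary analysis where the missing preparation evaluations", and goes on to count those evaluations as failures when colonoscopy was not done because of inadequate preparation or preparation-related adverse events. SAP 3.2.11 bases percentages on subjects with available data.

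**Population.** SAP 3.2.1 analyses these endpoints in the ITT set, which includes subjects who took only part of a dose.

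**The concern.** The lowest acceptability category is worded for a subject whose displeasure compromised use of the product. The other four describe subjects who took the complete dose or could be persuaded to. A subject who takes some of dose 1 and refuses dose 2 is in the ITT set and fits the lowest category for dose 2. But there is no dose-2 intake after which to complete a form, under either the protocol's timing or the SAP's. The dose-2 rating is then missing, the two-dose average cannot be formed, and nothing replaces it.

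Such a loss is unlikely to be random. Protocol 1.1 says that large-volume PEG solutions are often poorly tolerated because of taste and volume. The arms also differ in volume: 2250 mL in total for Eziclen/Izinova, against 70 mL/kg up to 4000 mL for Klean-Prep. If refusal differs between arms, the dose-2 and overall comparisons are made among those who went on to dose 2, and the arm with more refusal looks better than it should. Comparing acceptability is a named secondary objective (protocol 2.2.2), and the SAP will report treatment p-values for it.

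**Working it through.** **1. The plan's own figures.** The plan gives no figure for this point. Its sample size is needed only to turn percentages into counts. With 85% success in both arms, a margin of 15%, one-sided alpha of 0.025 and 90% power, n = (1.960 + 1.282)² × 2 × 0.85 × 0.15 / 0.15² = 119.1, rounded up to 120 per arm. With 4% dropout, 120 / 0.96 = 125. Both reproduce.

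**2. What each text yields.**

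| Situation | Protocol 7.3.2.3 | SAP 1.4.2.1 | Dose-2 rating |
|---|---|---|---|
| Dose 2 finished | form due | form due | present |
| Dose 2 started, then abandoned | unclear | form due | present under the SAP |
| Dose 2 never started | not covered | not covered | missing |

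The gap that neither text closes is the last row.

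**3. Inputs for an illustration.** Only the first has a source in the documents.
- Share f who never start dose 2: protocol 1.4 gives completion of the whole preparation in at least 93% of adults on the 1-day regimen of the test product, so up to 7% incomplete. This overstates f, because some of those who do not finish will have started dose 2. I set 7% in one arm against an assumed 2% in the other. At 7%, 0.07 × 120 = 8.4 and 0.07 × 125 = 8.75, so about 8 or 9 subjects in that arm.
- Mean overall score of completers: m = 3.0 in both arms (assumed).
- Dose-1 rating d of a refuser: 1, 2 or 3 (assumed). With dose 2 scored 1, the overall score is r = (d + 1)/2 = 1.0, 1.5 or 2.0.

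**4. Overall score.** The available-data mean is m in both arms, a difference of 0. The all-subject mean is (1 − f)m + f·r.
- r = 1.0: 2.86 against 2.96, difference 0.10
- r = 1.5: 2.895 against 2.97, difference 0.075
- r = 2.0: 2.93 against 2.98, difference 0.05

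In general the error is (f₁ − f₂)(m − r). It is zero if both arms lose the same share.

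**5. Wider assumptions.** With m from 3.0 to 4.0 and r from 1.0 to 1.5, the error is 0.08 to 0.15 for 7% against 2%, 0.12 to 0.24 for 15% against 7%, and 0.27 to 0.54 for 20% against 2%. Nothing in the documents supports the larger rates.

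**6. Dose-2 category table.** If no completer rates dose 2 in the lowest category, that category is understated by 7 points in one arm and 2 in the other, an error of 5 percentage points in the difference.

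**7. If one rating may stand for the average.** The SAP does not say so. On that reading the refuser keeps d as the overall score, and the error is 0.05 × (d − 1)/2 = 0, 0.025 or 0.05. The dose-2 comparison still loses the subject.

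**The case against.** The strongest reply is that the forms were never meant for finished doses alone. A reader might infer from the protocol's timing that only a completed dose is recorded, but the documents contradict that. The intake form asks for "residual volumes of preparation (volumes not taken by the subject" and for stop times, which would serve little purpose if every recorded dose were finished. The SAP, Table 5 and the Visit 1 procedures all allow a form for an abandoned dose. Subjects are in hospital, with a nurse or caregiver completing the forms or seeing that they are completed. All of this stands, and it narrows the gap to a dose never started and to an abandoned dose left unrated.

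A reader might also infer that the least compliant subjects leave the compliance analysis. The documents do not show that. Protocol 6.3 has dedicated staff assess compliance from measured unused preparation as well as the leaflet. SAP Appendix 1 (10) works from planned minus residual volume, and the compliance classes run down to below 50%. On a natural reading, a dose never started is a volume not taken. What is missing is only a sentence saying so.

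Other safeguards count too. Dose-1 acceptability is analysed on its own. A nasogastric tube is to be placed when a subject cannot complete the preparation, which shrinks the group by an unknown amount, and tube use is a separate endpoint tabulated by dose. Willingness to take the product again is also analysed. SAP 3.2.3.1 allows a pre-freeze decision with the sponsor where a subject has many missing values. That is a case-by-case decision, not a rule, and none of these items supplies a dose-2 or overall score.

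Finally, scoring a refusal as category 1 assigns a rating that nobody gave and requires a judgement on the reason. That is fair, and it is why a sensitivity analysis is an acceptable minimum.

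**Conclusion.** The point holds in a narrow form. The protocol and SAP time the forms differently, and neither covers a dose 2 that is never started. As written, subjects who refuse dose 2 drop out of the dose-2 and overall acceptability comparisons, which can bias these toward the arm with more refusal. On the illustrative inputs the overall arm difference is off by about 0.05 to 0.10 points on a 5-point scale, and by less with tube use. The 2% rate, the completer mean and the dose-1 ratings are assumptions, and the 7% is an adult upper bound for the test product.

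It would be tempting to infer that the acceptability and compliance objectives are reversed. The arithmetic does not show that: a small difference is hidden, and no sign changes. The compliance objective is to assess compliance in both arms. SAP 3.1.5 tests secondary endpoints for descriptive purposes only, and the primary endpoint has its own failure rule. This is a cheap improvement to a secondary analysis, not a threat to the trial's conclusion.

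**What to change.** 1. **Protocol 7.3.2.2 and 7.3.2.3, and the leaflet instructions.** Align with the SAP: both forms are completed when intake of each dose stops, whether or not the dose was finished.
2. **SAP 3.2.1.2.9.** Score a dose abandoned without a rating, or not started, for preparation-related reasons as category 1, and average it with the observed dose-1 rating. At minimum, do this as a sensitivity analysis beside the available-data result. Show the number of such subjects by arm. This follows the principle that the SAP already applies to the primary endpoint.
3. **SAP Appendix 1 (10).** State that a dose known not to have been started has residual volume equal to its planned volume. That is the actual value, not an imputation.

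The cost is a few sentences and one footnoted convention, which needs the reason for stopping. The SAP changes can be applied to forms already collected; the protocol change helps only forms still to be completed.
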